## 4 STUDY POPULATION AND STUDY PROCEDURES

### 4.1 Inclusion and exclusion criteria, justification of study population

A total of 12 healthy volunteers will be recruited for this study of which 6 males and 6 females.

#### Inclusion criteria

- Gender: male and female
- Age: 18-40 years
- Signed written informed consent

#### Exclusion criteria

- Smoking history
- Cardiovascular diseases
- BMI > 35 kg/m^2
- Caffeine consumption < 1 day before the study participation
- Allergies: Soy, Peas, Milk, Lactose, Fructose
- High intensity exercise <2 days before study participation

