Objective(s)	The objective of the study is to quantitatively assess the bioavailability of leucine in the blood following the consumption of a novel animal -and plant-based protein drink. This assessment will be compared to the bioavailability observed after consuming a commercially available animal-based protein drink. Leucine is the rate-limiting amino acid that drives protein synthesis in muscle and is associated with preservation of muscle mass during aging and inactivity. the study aims to determine whether the plant-based drink can match or exceed the bioavailability of amino acids typically seen in animal protein sources, thereby offering a viable nutritional alternative for those seeking plant-based diets.
Endpoint(s)	Leucine bioavailability in blood (Area Under the Curve)
Study Design	Exploratory, single center, randomized, single-blinded, cross-over controlled pilot study with three arms
Statistical Considerations	Repeated-measures ANOVA, sample size calculation is on the expected effect size based on previous literature, the desired level of statistical power (80%), and the significance level (0.05).
Inclusion- / Exclusion Criteria	Inclusion criteria: male and female, 18-40 years, signed written informed consent Exclusion criteria: smoking history, cardiovascular diseases, BMI > 35 kg/m  , allergies: Soy, Peas, Milk, Lactose, Fructose

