### 3.3 Study design

This will be an exploratory, single center, randomized, single-blinded, cross-over controlled pilot study with three arms: animal-based A, animal-based B, plant-based A. This study is designated as a 'pilot' because its objective is to generate scientifically valid data that can be leveraged for a more extensive future study focusing on older individuals experiencing malnutrition.

This trial design has the highest scientific validity as each participant will serve as their own control, and randomization determines the order in which the participants receive the drinks. The usual inter-subject variability is minimized by the cross-over design as each participant is used as their internal control as each drink is tested in every participant.

This study is a preliminary step (pilot) where we will examine how well leucine from various protein drinks is absorbed by people younger than 40 years old, as detailed in section 3.4. The findings from this initial study will help us design and carry out a more extensive, main study with older participants.

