#### Animal Drink A:

<https://www.fresenius-kabi.com/de-ch/produkte/fresubin-protein-energy-drink>

[https://www.fresubin.com/sites/default/files/2020-02/Productsheet\\_Fresubin%20Protein%20Energy\\_2019.pdf](https://www.fresubin.com/sites/default/files/2020-02/Productsheet_Fresubin%20Protein%20Energy_2019.pdf)

Average content		100 ml	bottle = 200 ml
Energy value	k.J (kcal)	630 (150)	1260 (300)
Fat	g	6.7	13.4
of which SFA*	g	0.6	1.2
of which MUFA**	g	4.9	9.8
of which PUFA***	g	1.2	2.4
Carbohydrate	g	12.4/12.1 a	24.8/24.2 a
of which sugars	g	6.5 a /6.9 a /7.1 a /7.4 a	13 a /13.8 a /14.2 a /14.8 a
of which lactose	g	≤ 0.4	≤ 0.8
Fibre	g	0/0.5 a	0/1.0 a
Protein	g	10.0	20.0
Salt (Na x 2.5)	g	0.13/0.15 a	0.26/0.30 a
Water	ml	79	158
Osmolarity	mosmol/l	380/390 a	
Minerals and trace elements			
Sodium	mg	50/60 a	100/120 a
Chloride	mg	73/58 a	146/116 a
Potassium	mg	130/135 a	260/270 a
Calcium	mg	205	410
Phosphorus	mg	120	240
Magnesium	mg	28/18 a	56/36 a
Iron	mg	2.5	5.0
Zinc	mg	2.0	4.0
Copper	μg	375	750
Iodine	μg	37.5	75.0
Selenium	μg	13.5	27
Manganese	mg	0.5	1.0
Chromium	μg	12.5	25.0
Molybdenum	μg	18.8	37.6
Fluoride	mg	0.25	0.5
Vitamins and othera substances			
Vitamin A	μg RE a	213	426
of which β-Carotene	μg RE a	63	126
Vitamin D 3	μg	2.5	5.0
Vitamin E	mg α-TE **	3.75	7.5
Vitamin K 1	μg	21	42
Vitamin C	mg	18.8	37.6
Thiamin (vitamin B 1 )	mg	0.3	0.6
Riboflavin (vitamin B 2 )	mg	0.4	0.8
Vitamin B 6	mg	0.43	0.86
Niacin	mg/mg NE ***	1.5 / 3.18	3.0 / 6.36
Folic Acid	μg	62.5	125.0
Vitamin B 12	μg	0.75	1.5
Pantothenic Acid	mg	1.5	3.0
Biotin	μg	9.4	18.8
Caffeine a	mg	0.65 a	1.3 a
Caloric distribution (energy%)			
Fat 40, carbohydrate 33/32.3 a , fibre 0/0.7 a , protein 27			
a = Flavour Cappuccino, b = Flavour Chocolate, c = Flavour Nut, d = Flavour Tropical Fruits, e = Flavour Vanilla, f = Flavour Wild Strawberry			
*saturated fatty acids (SFA), **monounsaturated fatty acids (MUFA),			
***polyunsaturated fatty acids (PUFA)			

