a retinol equivalents (RE), ** α-tocopherol equivalents (α-TE), *** niacin equivalents (NE)			

**Fresubin Protein Energy DRINK, flavour Wild Strawberry:** Water, milk protein, vegetable oils (sunflower oil, rapeseed oil), maltodextrin, sucrose, flavourings, potassium citrate, beetroot powder, emulsifiers (E 471, soya lecithins), sodium chloride, vit. C, magnesium oxide, magnesium citrate, iron pyrophosphate, zinc sulphate, manganese chloride, vit. E, pantothenic acid, niacin, copper sulphate, vit. B2, vit. B6, sodium fluoride, vit. B1, β-carotene, vit. A, folic acid, chromium chloride, potassium iodide, sodium molybdate, sodium selenite, vit. K1, biotin, vit. D3, vit. B12.

Animal Drink B		
Reference Unit	Unit	Content per 100 ml
Energy, Calories	kcal	150
Fat	g	6.6
Carbohydrates	g	12.7
- of which sugars	g	8.8
Protein	g	10

- of which leucine	g	1
Plant Drink A		
Reference Unit	Unit	Content per 100 ml
Energy, Calories	kcal	150
Fat	g	6.9
Carbohydrates	g	11.7
- of which sugars	g	8.4
Protein	g	10
- of which leucine	g	0.8

Vitamin and mineral content of drinks (same for Animal Drink B and Plant Drink A):

Nutrient	Unit	Content per 100 ml
Vitamin A (μg-RE)	μg	213
Sodium (mg)	mg	50
Vitamin D (μg)	μg	2.5
Potassium (mg)	mg	130
Vitamin E (mg α-TE)	mg	3.75
Chloride (mg)	mg	73
Vitamin K (μg)	μg	21
Calcium (mg)	mg	205
Vitamin C (mg)	mg	18.8
Phosphorus (mg)	mg	120
Thiamin (Vitamin B1) (mg)	mg	0.3
Magnesium (mg)	mg	28
Riboflavin (Vitamin B2) (mg)	mg	0.4
Iron (mg)	mg	2.5
Niacin (Vitamin PP) (mg NE)	mg	1.5
Zinc (mg)	mg	2
Vitamin B6 (mg)	mg	0.43
Copper (mg)	mg	0.375
Folic Acid (μg)	μg	62.5
Manganese (mg)	mg	0.5
Vitamin B12 (μg)	μg	0.73
Selenium (μg)	μg	13.5
Biotin (μg)	μg	9.4
Chromium (μg)	μg	12.5
Pantothenic Acid (mg)	mg	1.5
Molybdenum (μg)	μg	18.8
Iodine (μg)	μg	37.5
Fluoride (mg)	mg	0.25

Drinks will be manufactured in a Food Grade Laboratory, LFO, ETH Zurich using standard mixing and homogenization procedures. Drinks will be sterilized using pasteurization (heating to 80 °C for 1 min. Exact composition of the drinks will be verified by Eurofins Scientific (<https://www.eurofins.com/>)

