Participants will arrive fasted at the lab. After a 60 min seated rest, a baseline blood sample will be taken 30 minutes prior to consuming the drink. After consuming the assigned drink, a second, third and fourth blood sample will be collected 30, 60 and 90 minutes later, to determine leucine appearance (Area Under the Curve, AUC). This procedure will be repeated three times, each with a different drink, with 5-7 days washout in between. The primary measure of the study is the leucine content in the blood, determined using High-Performance Liquid Chromatography (HPLC), to assess the bioavailability of the proteins in the drinks.

We are testing two kinds of animal-based protein drinks and one plant-based protein drink. The reason for this is we are creating alternatives to the nutritional drinks currently sold by companies like Nestlé and Fresubin (FSMP products). We have made a drink using whey (which comes from animals) and another using a combination of pea and rice (which are plants), ensuring both have the same mix of nutrients as the ones you can buy now. We want to see if our drinks are better at delivering leucine to the body compared to the existing products.

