### 4.2 Recruitment, screening and informed consent procedure

The participant recruitment will occur using advertisements and social media within the Zurich area. The investigators will explain to each participant the nature of the study, its purpose, the procedures involved, the expected duration, the potential risks and benefits and any discomfort it may entail. Each participant will be informed that the participation in the study is voluntary and that he or she may withdraw from the study at any time and that withdrawal of consent will not have any consequences. All participants for the study will be provided a participant information sheet and a consent form describing the study and providing sufficient information for participant to make an informed decision about their participation in the study. One week time will be given to the participant to decide whether to participate or not. The formal consent of a participant, using the approved consent form, will be obtained before the participant is submitted to any study procedure.

The consent form will be signed and dated by the investigator or his designee at the same time as the participant signs. A copy of the signed informed consent will be given to the study participant. The consent form will be retained as part of the study records. After potential participants have given their informed consent, the project leader will accurately verify again the inclusion and exclusion criteria of the study. If all inclusion and exclusion criteria are fulfilled, participants will be included in the study. Study participants will receive CHF 100 for their participation into the study, after completion of the third experimental arm.

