###### **2. Lab Visits (Months 2-3):**

Participants will undergo three lab visits at Laboratory Exercise and Health, D-HEST, [name]

- Participants will arrive fasted at the lab (no food and beverages starting at midnight)
- Each lab visit involves a 60-minute seated rest, followed by blood sample collection minutes before consuming the drink and 30, 60 and 90 minutes after consuming the assigned drink (see point 3. below).
- Three following three different drinks will be administered in a randomized order, with 5-7 days washout between visits:
  - Animal-based A: A commercially available high protein drink, based on animal proteins (Fresubin Protein Energy).
  - Animal-based B: A homemade drink containing animal-based proteins
  - Plant-based B: A homemade drink containing plant-based proteins, formulated to have the same macronutrient content as the animal-based drinks.
- All ingredients of the drink are food grade and prepared at a food-grade level (Laboratory of Sustainable Food Processing, ETH Zurich). Exact ingredients are: Plant protein isolates (pea, rice, hemp, pumpkin), Animal-based isolates (whey) water, maltodextrin, fruit puree (raspberry). All ingredients are commercially available.
- Total volume of the drink will range from 250ml to 400ml depending on the bodyweight of the participant
- During the first visit there will be also a short assessment of participants' characteristics (i.e. sociodemographic data and self-reported physical activity level). The following characteristics will be collected by the project leader/study personnel, inserted in a dedicated electronic Case Report Form (eCRF) within a web-based Electronic Data Capture (REDCap) system.

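### The allergy exclusion is a closed five-item list that omits rice and other named drink ingredients, so a volunteer with a known allergy to one of them is eligible as written

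*Combined protocol and SAP*

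**What the plan says.** The exclusion criteria in section 4.1 of the combined protocol and SAP contain one allergy item: "Allergies: Soy, Peas, Milk, Lactose, Fructose". The synopsis carries the same five: "allergies: Soy, Peas, Milk, Lactose, Fructose". Neither has wording that marks the items as examples or extends them to other ingredients.

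The plant drink is described twice. Section 3.4 refers to one homemade drink made from whey and "another using a combination of pea and rice (which are plants". Section 4.3 (Lab Visits) gives a longer list for the homemade drinks: "Exact ingredients are: Plant protein isolates (pea, rice, hemp, pumpkin), Animal-based isolates (whey) water, maltodextrin, fruit puree (raspberry".

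For the commercial drink, section 3.4 shows one recipe, for the Wild Strawberry flavour. It begins: "Water, milk protein, vegetable oils (sunflower oil, rapeseed oil), maltodextrin, sucrose, flavourings, potassium citrate, beetroot powder, emulsifiers (E 471, soya lecithins".

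On enrolment, section 4.2 has the project leader verify the criteria again after consent and then states: "If all inclusion and exclusion criteria are fulfilled, participants will be included in the study". Under section 3.3, "each drink is tested in every participant".

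**The concern.** The synopsis gives two study risks, and allergic reaction to the drinks is one of them. The natural control for a risk that is foreseen and named is an eligibility criterion. Here that criterion covers some of what participants will drink and leaves the rest out.

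The selection has no stated logic. Soy is listed, and its only named source in the drinks is an emulsifier in the commercial product. Rice, a protein source of the plant drink, is not listed. Pea and rice are both protein isolates in that drink, but only pea is covered.

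Because this is a crossover trial, nobody who completes it avoids the plant drink. At stake is the safety of an individual volunteer with a known allergy to an unlisted ingredient, and the correctness of the eligibility decision for that person.

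**Working it through.** No arithmetic applies, and the plan has no figure of its own to reproduce on this point. The check sets the exclusion list against each food source named in the drinks.

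| Food source | Where named | On the list? |
|---|---|---|
| Pea | sections 3.4 and 4.3 | yes (peas) |
| Rice | sections 3.4 and 4.3 | no |
| Hemp, pumpkin | section 4.3 only | no |
| Raspberry puree | section 4.3 only | no; the fructose item touches it only as a sugar |
| Whey, milk protein | sections 3.4 and 4.3 | yes (milk) |
| Soya lecithins | section 3.4, commercial recipe | yes (soy) |
| Sunflower oil, rapeseed oil | section 3.4, commercial recipe | no |
| Beetroot powder | section 3.4, commercial recipe | no; may be specific to this flavour |

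Step 1. Rice is in the plant drink whichever description is right, and it is not on the list. The point therefore does not depend on settling the difference between sections 3.4 and 4.3.

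Step 2. Hemp, pumpkin and raspberry are unlisted too, but they rest on section 4.3 alone.

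Step 3. The commercial recipe adds further unlisted ingredients. The product table in section 3.4 covers six flavours, among them "c = Flavour Nut, d = Flavour Tropical Fruits, e = Flavour Vanilla, f = Flavour Wild Strawberry", and only the Wild Strawberry recipe is printed. What another flavour would add cannot be read from the documents.

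Step 4. The reviewed text contains no criterion for other drink ingredients, no exclusion at the investigator's discretion and no allergy screening step.

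Step 5. Apply the rule in section 4.2 to a volunteer aged 18 to 40 who has a known rice allergy and is otherwise unremarkable. All inclusion criteria are met and no exclusion applies, so the rule includes that person.

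Step 6. Look for another provision that would stop enrolment. Section 7.2 says that ingredients were chosen for low allergenic potential, that composition is disclosed during consent, and that allergen questions are dealt with. Section 4.2 gives a week to decide. Section 4.3 has a nurse draw blood 30, 60 and 90 minutes after each drink. None of these makes the person ineligible. The blood draws come after exposure and are not described as monitoring for reactions.

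**The case against.** The strongest reply is that harm needs an unlikely chain. A volunteer would have to know of a rice allergy, be told that the drink contains rice, have a week to think, and still drink it. The investigator would have to allow this despite the commitment to GCP and the Declaration of Helsinki in section 6.1. The proposed criterion would still rest on self-report. The information sheet and consent form are not in the reviewed copy and may already ask about ingredients. All of this stands as an argument for low practical risk, and it is why the point is minor. It does not change the eligibility rule, which as written gives the wrong answer for such a volunteer.

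A second reply is that excluding intolerance goes further than allergy. That carries little weight, because lactose and fructose are already on the list.

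A reader might infer more than the documents support, in two ways:

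- One could count unlisted against listed ingredients and read the ratio as the size of the gap. That count would treat an oil like a protein isolate. It would also rest on an incomplete recipe: section 4.3 names no fat source, although section 3.4 gives the homemade drinks 6.6 and 6.9 g of fat per 100 ml.
- One could conclude that allergic volunteers will in practice be given the drinks without being asked. The documents do not show that, given the consent steps in section 7.2 and the pages that are not available here.

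**Conclusion.** The point holds as a gap in a stated rule. The allergy exclusion is closed, it omits rice under both descriptions of the plant drink, and it omits hemp, pumpkin and raspberry under section 4.3. It also omits some named ingredients of the commercial recipe shown. A volunteer with a known allergy to any of these meets the written criteria.

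Its weight is that of a minor safety correction. It has no bearing on the endpoint, the analysis or the sample size. The documents give no allergy frequencies, so the risk is not quantified. The conclusion assumes that the criteria in section 4.1 are applied as written and that no further allergy criterion stands in material outside the reviewed copy. Confidence is high for the wording gap and lower for its practical consequence.

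**What to change.** In the synopsis and in section 4.1, replace the allergy item with: *Known allergy or intolerance to any ingredient of any study drink (for example soy, peas, milk, lactose, fructose, rice).* Make this a required question when the project leader verifies the criteria under section 4.2. No allergy testing is needed. A disclosure that the text now leaves to the volunteer becomes a question that must be asked, with a firm exclusion behind it. The wording also stays correct if the recipe or the commercial flavour changes.

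It would help, though the point does not depend on it, to make sections 3.4 and 4.3 agree on the plant proteins and to state which commercial flavour is used.

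The cost is a few words, one question, and an occasional volunteer turned away and replaced to reach the 12 in section 4.1. Section 6.4 treats changes that affect participants' safety as substantial and requires Ethics Committee approval before they take effect. If version 3.0 is already approved, this change may need that step.

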### 4.2 Recruitment, screening and informed consent procedure

The participant recruitment will occur using advertisements and social media within the Zurich area. The investigators will explain to each participant the nature of the study, its purpose, the procedures involved, the expected duration, the potential risks and benefits and any discomfort it may entail. Each participant will be informed that the participation in the study is voluntary and that he or she may withdraw from the study at any time and that withdrawal of consent will not have any consequences. All participants for the study will be provided a participant information sheet and a consent form describing the study and providing sufficient information for participant to make an informed decision about their participation in the study. One week time will be given to the participant to decide whether to participate or not. The formal consent of a participant, using the approved consent form, will be obtained before the participant is submitted to any study procedure.

The consent form will be signed and dated by the investigator or his designee at the same time as the participant signs. A copy of the signed informed consent will be given to the study participant. The consent form will be retained as part of the study records. After potential participants have given their informed consent, the project leader will accurately verify again the inclusion and exclusion criteria of the study. If all inclusion and exclusion criteria are fulfilled, participants will be included in the study. Study participants will receive CHF 100 for their participation into the study, after completion of the third experimental arm.

#### **4.3 Study procedures**

##### **Overall Project Duration:**

The project encompasses a total duration of four months, inclusive of the recruitment period and participation for each study subject. All the study procedures are summarized with a time schedule in Table 1.

##### **Sequence of Planned Procedures:**

###### **1. Recruitment and screening (Month 1)**

Recruitment and screening are projected to span one month, with the goal of enrolling 14 study participants.

- Participants will be recruited through advertisements and social media.
- Screening procedures will ensure eligibility criteria are met.

###### **2. Lab Visits (Months 2-3):**

Participants will undergo three lab visits at Laboratory Exercise and Health, D-HEST, [name]

- Participants will arrive fasted at the lab (no food and beverages starting at midnight)
- Each lab visit involves a 60-minute seated rest, followed by blood sample collection minutes before consuming the drink and 30, 60 and 90 minutes after consuming the assigned drink (see point 3. below).
- Three following three different drinks will be administered in a randomized order, with 5-7 days washout between visits:
  - Animal-based A: A commercially available high protein drink, based on animal proteins (Fresubin Protein Energy).
  - Animal-based B: A homemade drink containing animal-based proteins
  - Plant-based B: A homemade drink containing plant-based proteins, formulated to have the same macronutrient content as the animal-based drinks.
- All ingredients of the drink are food grade and prepared at a food-grade level (Laboratory of Sustainable Food Processing, ETH Zurich). Exact ingredients are: Plant protein isolates (pea, rice, hemp, pumpkin), Animal-based isolates (whey) water, maltodextrin, fruit puree (raspberry). All ingredients are commercially available.
- Total volume of the drink will range from 250ml to 400ml depending on the bodyweight of the participant
- During the first visit there will be also a short assessment of participants' characteristics (i.e. sociodemographic data and self-reported physical activity level). The following characteristics will be collected by the project leader/study personnel, inserted in a dedicated electronic Case Report Form (eCRF) within a web-based Electronic Data Capture (REDCap) system.

